### 7.3 Analyses

Point estimates and confidence interval will be calculated for all dichotomous endpoints (N0 control rate, locoregional control rate, AE specific rates). The Kaplan-Meier product-limit method will be used to estimate PFS and locoregional recurrence-freesurvival. Confidence intervals will be estimated for all efficacy endpoints. Under the assumption of exponential PFS we will estimate the exponential parameter ( $\lambda$ ) and test whether the data support the alternative hypothesis that  $\lambda=0.1335$  versus the null hypothesis that  $\lambda=0.0744$ . Repeated measure models will be used to describe the change over time in QOL as measured by questionnaire. Data from the treatment planning software which produces graphs on mean, max, minimum doses to structures, as well as volumes of particular structures receiving certain doses will be used to compare the dose volume histograms (DVH) of treatment plans for patients receiving 39.6 Gy to the N0 neck to the DVH of matched treatment plans with the standard 50 Gy to the

N0 neck (i.e., to quantify the difference in radiation dose to critical structures in the neck with the decreased dose regimen compared to standard practice).

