### **1.3.5 Post-treatment Surveillance with PET-CT**

Patients with head and neck cancer are often monitored after treatment with PET CT, as it has been shown to be highly sensitive in the detection of persistent and recurrent disease after treatment(50-52). Multiple studies show that an initial negative PET CT obtained 3 months after definitive radiotherapy can have a negative predictive value (NPV) as high as 100% for locoregional recurrence with an average NPV of 95%(50-52). However, sensitivity of PET is slightly lower for distant metastases(51, 52). Most authors recommend follow-up PET CT from 3 to 6 months after completion of treatment because studies have shown higher false-negative PET scans when obtained less than 3 months after treatment(50, 51, 53, 54). Thus, a negative PET scan 3 to 6 months after treatment may have a very high probability of ruling out any locoregional recurrence in patients who receive a lower dose to the N0 neck.

If a locoregional recurrence is going to occur, it is most likely to recur within 1 to 2 years, as nearly 90% of all HNC failures occur within the first 2 years after treatment(36). Yao et al (2005) found that 11/150 (7.3%) HNC

patients treated with IMRT developed locoregional recurrences in a median time of about 5 months (range of 2 to 16 months)(37). Their local recurrence-free survivals at 2 and 3 years were equivalent at 94%, and locoregional recurrence-free survivals at 2 and 3 years were also equivalent at 92%. Eisbruch et al reported a 16% rate of locoregional recurrence at a median time of 8 months (55), while Huang et al (2008) reported 10% developing locoregional recurrences at a median time of 15 months (range of 3 to 43 months)(31). Thus, any patient disease-free at 2 years has a very high likelihood of remaining disease-free. However, data is not available for the recurrence of the N0 volumes in the above studies, and they did not stratify their data according to p16 status, which provides vital prognostic significance. Our p16+ patients had 100% control of the N0 volumes at 3 years after treatment, so any isolated recurrence in the N0 volumes after dose reduction at any time in this current study would be suspicious for an inferior treatment.

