### **6.2.2 Progression-Free Survival**

Progression-Free Survival (PFS) is defined as the duration of time from start of treatment to time of recurrence/progression or death from any cause, whichever occurs first. Progression will be measured as defined by the RECIST criteria (Section 6.1). Patients who do not experience an event (recurrence/progression or death) will be censored at date of last contact.

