## **7.2 Sample Size and Accrual**

We know of no detailed published data for the primary and secondary endpoints for the study specific p16+/HPV+ OP-SCCA patient population of interest. However, the ‘historical’ data from sixty patients (updated since publication) treated at UVA provides us with a reliable source to guide sample size determination and monitoring guidelines. For those sixty patients, N0 recurrence occurred in 1/60=1.7% and locoregional failure occurred in 6/60=10% with the upper limit of a one-sided 95% CI being 7.7% and 19%, respectively. Three-year PFS from start of radiation treatment is 80% (95% CI (67, 88%)). For sample determination, these estimates will be used to define the null and alternative 3-

year PFS rates. Specifically, we would like to be able to differentiate between a null 3-year PFS rate of 80% versus the alternative of 67%. Assuming uniform accrual of 15 eligible patients a year for 3 years, a minimum follow-up time of 3 years, PFS is exponentially distributed, a one-sided 10% level test then accrual of 45 eligible patients provides approximately 89% power at the alternative. If the exponential assumption is not supported by the data then accrual of 45 eligible patients results in 80% power to test for a decrease of 14% in 3-year PFS with a one-sided 10% exact binomial level test.

A sequential probability ratio test (SPRT) based upon a binomial test of proportions for N0 control rates will be used. Only the upper boundary will be used for monitoring to protect against excessive failures. The stopping boundary are for a SPRT contrasting a 2% versus 8% N0 control rate, with nominal type I and II errors of 10% and 10%, respectively. The slope of the parallel lines for monitoring is 0.043 and the intercepts are 1.516 and 1.516.

Stopping guideline for N0 Failure	
Number of participants	Boundary
2-9	$\geq 2$
10-33	$\geq 3$
34-45	$\geq 4$

For estimation of locoregional control, a sample size of 45 eligible patients produces a two-sided 90% confidence interval with a width equal to 0.17 when the sample proportion is assumed at the observed historical rate of 10%.

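### The 3-year PFS test assumes a constant hazard; its 89% power needs exponential PFS and 3–6 years of follow-up, and the fallback test has no stated trigger or censoring rule

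*Combined protocol and SAP*

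**What the plan says.** Section 7.2 sizes the trial to separate a "null 3-year PFS rate of 80% versus the alternative of 67" percent. The conditions are explicit: "Assuming uniform accrual of 15 eligible patients a year for 3 years, a minimum follow-up time of 3 years, PFS is exponentially distributed". Under them, "a one-sided 10% level test then accrual of 45 eligible patients provides approximately 89% power at the alternative". Section 7.3 turns this into a test of a hazard of 0.0744 against 0.1335: "Under the assumption of exponential PFS we will estimate the exponential parameter".

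Section 7.2 also gives a fallback: "If the exponential assumption is not supported by the data then accrual of 45 eligible patients results in 80% power". That power is for a 14-point fall in 3-year PFS, tested by an exact binomial test at one-sided 10%.

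Other sections bear on the test:
- Section 1.3.5, on post-treatment surveillance, says that "nearly 90% of all HNC failures occur within the first 2 years after treatment".
- Section 4.7 ends each patient's follow-up three years after treatment.
- Section 6.2.2 sets the censoring rule for PFS: "Patients who do not experience an event (recurrence/progression or death) will be censored at date of last contact".
- Section 7.3 already plans Kaplan-Meier estimates of PFS with confidence intervals, but does not tie them to the test.

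**The concern.** A hazard test and a 3-year PFS test ask the same question only if the hazard is constant. If failures come early and then level off, event-free time after year 3 dilutes the estimated rate, and the test under-reports poor 3-year PFS. The null is the historical 80% and the alternative is worse, so lost power means failing to notice that PFS has deteriorated under the reduced nodal dose.

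PFS is a secondary endpoint. But it set the sample size, and section 7.1 makes a 3-year survival result no worse than historical (called disease-free survival there) a condition for further study. Whether the fallback is used, and how it counts a patient lost before 3 years, could decide that result. Neither is written down.

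**Working it through.** **Inputs.** N = 45, one-sided 10%, 3-year PFS 80% and 67%, accrual over 3 years with minimum follow-up of 3 years (section 7.2); hazards (7.3); follow-up of 3 years after a 7-week course (4.6, 4.7). Assumptions, not in the documents: the exact failure pattern, the loss rates and the form of the fit check.

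**1. Reproduce the plan.** Hazards: −ln(0.80)/3 = 0.0744 and −ln(0.67)/3 = 0.1335; both agree. With follow-up uniform on 3–6 years, expected events are 45 × [1 − (e^(−3λ) − e^(−6λ))/(3λ)]:
- null: 45 × [1 − (0.80 − 0.64)/0.2231] = 12.7
- alternative: 45 × [1 − (0.67 − 0.4489)/0.4005] = 20.2

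The test rejects if ln(λ̂/0.0744) × √d > 1.2816, where d is the number of events. Simulation gives level 10.9% and power 87.2%. The most favourable approximation is Φ(0.5848 × √20.16 − 1.2816) = 91%, where 0.5848 = ln(0.1335/0.0744). Using the null variance only, Φ(0.5848 × √12.73 − 1.2816) = 79%. The stated 89% lies inside this range.

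**2. Follow-up as in section 4.7.** 3 + 7/52 = 3.13 years from start. Expected events fall to 9.3 and 15.4. Under exponential PFS, simulated power is 80% (level 11%). The approximation that gave 91% now gives Φ(0.5848 × √15.38 − 1.2816) = 84%.

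**3. Front-loaded failures.** Under the plan's exponential curves, the share of 3-year failures falling by year 2 is (1 − e^(−2λ))/(1 − e^(−3λ)) = 69% (null) and 71% (alternative). To represent section 1.3.5, assume 90%, with 3-year PFS unchanged:
- null: S(2) = 1 − 0.9 × 0.20 = 0.82; hazard −ln(0.82)/2 = 0.099 to year 2, then ln(0.82/0.80) = 0.025
- alternative: S(2) = 1 − 0.9 × 0.33 = 0.703; hazard 0.176, then 0.048

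Exponential test alone, simulated:

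| Follow-up | Pattern | Level | Power at 67% |
|---|---|---|---|
| 3–6 y | exponential | 10.9% | 87% |
| 3–6 y | 80% by year 2 | 6% | 78% |
| 3–6 y | 90% by year 2 | 3.2% | 64% |
| 3.13 y | exponential | 11.3% | 80% |
| 3.13 y | 90% by year 2 | 10.8% | 79% |
| 3.0 y | 90% by year 2 | 12.5% | 80% |

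**4. The binomial fallback, no losses.** P(X ≥ 13 | 45, 0.20) = 0.0995 and P(X ≥ 12) = 0.174, so the cut is 13 failures. Power is 0.810 at 34% failures (the 14-point fall; the stated 80% reproduces) and 0.769 at 33%, the design alternative.

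**5. The two-step procedure.** No fit check is specified, so assume a 5% likelihood-ratio test of a two-piece against a constant hazard. Under the 90% pattern it flags the departure in 54% (null) to 69% (alternative) of trials with 3–6 years of follow-up, and in 39–45% with 3 years. Switching to the binomial when flagged:

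| Follow-up | Level | Power at 67% |
|---|---|---|
| 3–6 y | 9.2% | 75% |
| 3.13 y | 10.5% | 78% |
| 3.0 y | 11.0% | 79% |

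**6. Patients censored before 3 years.** Binomial level and power at a 14-point fall, exponential PFS, for assumed losses of 5% and 10%:

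| Lost patients are | 5% lost | 10% lost |
|---|---|---|
| counted event-free | 8.5% / 78% | 7.3% / 74% |
| excluded | 8.7% / 78% | 9.2% / 78% |
| counted as failures | 27% / 91% | 50% / 96% |

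At 67% with the front-loaded pattern, 10% lost and counted event-free gives about 71%.

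**7. A Kaplan-Meier test at 3 years.** On the complementary log-log scale, Z = [ln(−ln Ŝ) − ln(−ln 0.80)] / [√V/|ln Ŝ|], with V the Greenwood sum. With no losses, V = d/[n(n − d)]:
- 13 failures: Ŝ = 32/45, V = 13/(45 × 32), Z = 1.52, above 1.2816
- 12 failures: Ŝ = 33/45, V = 12/(45 × 33), Z = 1.14, below it

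The cut is again 13, so level and power equal the binomial's: 9.9% and 77%. With assumed 10% loss, power at 67% is about 76%. With 20% loss it is about 75%, at a level of about 11%.

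**The case against.** The plan anticipated this problem. The 89% is stated as conditional on exponential PFS, it reproduces, and the next sentence supplies a test that needs no hazard shape. A reader might infer that the 10% level and 89% power are miscalculated, or that the switch fails to rescue the analysis. The documents support neither. Under the 90% pattern, the two-step procedure keeps the level near 10%, and its power is within about 2 points of the Kaplan-Meier test. The figures of 3% and 64% belong to the exponential test alone, which the plan would often replace.

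A reader might also infer that the binomial test cannot deal with censored patients. What is missing is a rule. All patients are planned for 3 years of follow-up, and with complete data the test is exact.

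Finally, the 90% figure describes all head and neck cancer failures, in a paragraph on locoregional recurrence. PFS also counts deaths from any cause, and these patients are p16+. Section 1.3.5 does not contradict exponential PFS; it makes it doubtful.

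All of this stands. It leaves three gaps: the 89% does not fit the follow-up in section 4.7, the switch has no criterion, and early censoring has no rule in the fallback.

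**Conclusion.** The point holds as a specification weakness, not an arithmetic error. Of the scenarios examined, only exponential PFS with 3–6 years of follow-up comes near 89%. With the follow-up in section 4.7, power is about 79–80%, and there the hazard shape hardly matters. With 3–6 years and 90% of 3-year failures by year 2, the exponential test alone drops to about 3% level and 64% power. The fallback brings this back to about 9% and 75%, assuming a 5% likelihood-ratio check and no losses. The fallback's own power at the design alternative is 77%, not 80%, because the 80% is for a 14-point fall and the design is for 13.

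The error does not always go one way. The level falls with long follow-up and rises modestly (to 12.5% under this pattern) if follow-up stops at exactly 3 years. The size of the front-loading and the loss rates are assumptions. The undefined trigger, the missing censoring rule and the follow-up mismatch are not. The plan should be changed, although PFS is secondary.

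**What to change.** In section 7.3, make the PFS decision test a single prespecified one-sided 10% test of the Kaplan-Meier 3-year estimate against 80%, on the complementary log-log scale. It needs no hazard shape, uses censored patients up to last contact as section 6.2.2 intends, and does not depend on follow-up after year 3. Keep the exponential test as a sensitivity analysis and drop the data-driven switch. In section 7.2, restate power as about 77% at 67%, and reconcile the follow-up assumed there with section 4.7.

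The cost is wording only: no added patients or visits, since the Kaplan-Meier analysis is already planned. The downsides are a stated power about 12 points lower (89% to 77%), some loss of power against the exponential test if PFS really is exponential with 3–6 years of follow-up (87% against 77%), and a level that is only approximate when patients are lost (about 11% at an assumed 20% loss).

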#### **7.4 Reporting and Exclusions**

All patients will be evaluable for toxicity and adverse events from the time of protocol intervention (start of treatment).

Evaluation of efficacy – All patients included in the study should be assessed for efficacy endpoints, even if there are major protocol treatment deviations or if they are ineligible. All of the patients who met the eligibility criteria will be included in the main analysis of the efficacy.

### **8 ADVERSE EVENTS AND REPORTING**

Adverse events will be collected from the initiation of the radiation treatment until at least 30 days following completion of study treatment (i.e. end of seven week regimen or date of discontinuation). All adverse events should be reviewed by the treating physician to determine if expedited reporting is required. The following sections provide definitions for adverse event characteristics and reporting requirements.

#### **8.1 Definitions**

##### **8.1.1 Adverse Event**

An adverse event is any undesirable medical experience occurring to a subject who has been given an investigational product, whether or not related to the study drug(s). Medical conditions present before starting the investigational drug/intervention will be considered adverse events only if they worsen after starting study treatment. The following are adverse events:

- All unfavorable, harmful or pathological changes in the general condition of a patient.
- Subjective or objective symptoms (spontaneously offered by the patient and/or observed by the Investigator or the study nurse).
- All intercurrent events or exacerbation of pre-existing diseases which occurred after the administration of the study drug.
- All clinically significant changes in laboratory abnormalities.
- Any undesirable and unintended effect of research occurring in human subjects as a result of the collection of identifiable private information under the research.

AEs should be followed to resolution or stabilization, and reported as SAEs if they become serious (see below, definition of SAE). This also applies to patients experiencing AEs that cause interruption or discontinuation of investigational product, or those experiencing AEs that are present at the end of their participation in the study. Such patients should receive post-treatment follow-up as appropriate. AEs will be collected at least for 30 days post last day of radiation treatment in all cases including early study termination. If an ongoing AE changes in its severity or in its perceived relationship to study drug, a new AE entry for the event should be completed.

### 8.1.2 Expectedness

The expectedness of the adverse event will be determined by the Investigator based on current literature and the Investigator's experience. Below is a listing of the adverse events, and maximum grade of event, expected in this study:

Adverse Events with Possible Relationship to Study Treatment			Maximum Grade
Likely (>20%)	Less Likely (<=20%)	Rare but Serious (<3%)	
BLOOD AND LYMPHATIC SYSTEM DISORDERS			
Anemia			1
	Anemia		2
Lymphopenia			2
Lymph Node Pain			1
	Lymph Node Pain		2
CARDIAC DISORDERS			
	Tachycardia (any type)		2
EAR AND LABYRINTH DISORDERS			
Ear Pain			1
	Ear Pain		2
		Ear Pain	3
Hearing Impaired			1
	Hearing Impaired		2
		Hearing Impaired	3
Middle Ear Inflammation			2
Tinnitus			1
	Tinnitus		2
		Tinnitus	3
	Vertigo		1
		Vertigo	2
ENDOCRINE DISORDERS			
Hypothyroidism			1
	Hypothyroidism		2
EYE DISORDERS			
	Cataract		1
	Conjunctivitis		1
		Retinopathy	2
	Watering Eyes		1
GASTROINTESTINAL DISORDERS			
Dental Caries			2

	Dental Caries		3
Dry Mouth			2
	Dry Mouth		3
Dysphagia			3
		Dysphagia	4
Esophageal Stenosis			1
	Esophageal Stenosis		3
		Esophageal Stenosis	4
Gingival Pain			2
Lip Pain			1
	Lip Pain		2
Mucositis Oral			3
Nausea			2
	Nausea		3
Oral Pain			3
	Peridental Disease		3
Salivary Duct Inflammation			2
	Salivary Duct Inflammation		3
	Toothache		2
Vomiting			1
	Vomiting		3
GENERAL DISORDERS AND ADMINISTRATION SITE CONDITIONS			
Edema Face			1
	Edema Face		2
		Edema Face	3
Fatigue			3
Irritability			2
	Irritability		3
Neck Edema			1
	Neck Edema		2
		Neck Edema	3
Pain Generalized			2
INFECTIONS AND INFESTATIONS			
Mucosal Infection			2
	Mucosal Infection		3
	Otitis Media		2
	Sinusitis		2
	Soft Tissue Infection		2
	Tooth Infection		2
	Tracheitis		2
	Upper Respiratory Infection		2
		Upper Respiratory Infection	3
INJURY, POISING AND PROCEDURAL			
Dermatitis Radiation			2
	Dermatitis Radiation		3
	Injury to Carotid Artery		3
		Injury to Carotid Artery	4
INVESTIGATIONS			
Creatinine Increased			1 1
	Creatinine Increased		2 2
Lymphocyte Count Decreased			2
	Lymphocyte Count Decreased		3
	Platelet Count Decreased		1

		Platelet Count Decreased	2
Weight loss			1
	Weight Loss		2
		Weight Loss	3
White Blood Cell Decreased			1
	White Blood Cell Decreased		2
		White Blood Cell Decreased	3
METABOLISM AND NUTRITION DISORDERS			
Anorexia			3
		Anorexia	4
Dehydration			1
	Dehydration		2
		Dehydration	3
	Hyperkalemia		1
		Hyperkalemia	2
	Hypercalcemia		1
		Hypercalcemia	2
	Hypomagnesemia		1
		Hypomagnesemia	2
	Hyponatremia		1
		Hyponatremia	2
MUSCULOSKELETAL AND CONNECTIVE TISSUE DISORDERS			
Generalized muscle weakness			1
		Head Soft Tissue Necrosis	3
Neck Pain			2
	Neck Pain		3
	Osteonecrosis of Jaw		2
		Osteoradionecrosis of Jaw	3
Trismus			1
	Trismus		2
		Trismus	3
NEOPLASMS BENIGN, MALIGNANT AND UNSPECIFIED			
	Treatment-related Second Malignancy		3
		Treatment-related Second Malignancy	4
Tumor Pain			2
	Tumor Pain		3
NERVOUS SYSTEM DISORDERS			
	Brachial Plexopathy		1
		Brachial Plexopathy	2
		Central Nervous System Necrosis	3
Dysguesia			2
Lethargy			1
	Lethargy		2
	Myelitis		1
		Myelitis	2
		Stroke	3
		Syncope	3
PSYCHIATRIC DISORDERS			
Agitation			1
	Agitation		2
Anxiety			2

	Anxiety		3
Depression			1
	Depression		2
		Depression	3
Insomnia			2
	Insomnia		3
Libido decreased			1
	Libido decreased		2
RESPIRATORY, THORACIC AND MEDIASTINAL DISORDERS			
Aspiration			2
	Aspiration		3
		Aspiration	4
Cough			2
	Cough		3
	Dyspnea		2
Hoarseness			1
	Hoarseness		2
Laryngeal Edema			1
	Laryngeal Edema		2
		Laryngeal Edema	4
Laryngeal Mucositis			3
Nasal Congestion			1
	Nasal Congestion		2
		Nasal Congestion	3
Pharyngeal Mucositis			3
		Pharyngeal Necrosis	4
Pharyngolaryngeal Pain			2
	Pharyngolaryngeal Pain		3
		Stridor	3
Tracheal Mucositis			1
	Tracheal Mucositis		2
		Tracheal Mucositis	3
SKIN AND SUBCUTANEOUS TISSUE DISORDERS			
Alopecia			1
Pain of Skin			2
	Pain of Skin		3
Skin Atrophy			1
	Skin Hyperpigmentation		2
Skin Induration			1
	Skin Induration		2
		Skin Induration	3
Telangiectasia			1
VASCULAR DISORDERS			
Hypotension			1
	Hypotension		2
		Hypotension	3
Lymphedema			1
	Lymphedema		2
		Lymphedema	3

### 8.1.3 Severity

The descriptions and grading scales found in the revised NCI Common Terminology Criteria for Adverse Events (CTCAE) version 4.0 will be utilized for AE reporting. All appropriate treatment areas should have access to a copy of the CTCAE version 4.0. A copy of the CTCAE version 4.0 can be downloaded from the CTEP web site (<http://ctep.cancer.gov>).

To assess severity of adverse events not included in the CTCAE version 4.0, use **Table 3** below.

**Table 3.** Adverse Event Severity Grading Scale for Adverse Events Not Specifically Listed in the NCI CTCAE

Grade	Severity
1	Mild; asymptomatic or mild symptoms; clinical or diagnostic observations only; intervention not indicated.
2	Moderate; minimal, local or noninvasive intervention indicated; limiting age-appropriate instrumental ADL 
3	Severe or medically significant but not immediately life-threatening; hospitalization or prolongation of hospitalization indicated; disabling; limiting self care ADL 
4	Life-threatening consequences; urgent intervention indicated.
5	Death related to AE

Instrumental ADL refer to preparing meals, shopping for groceries or clothes, using the telephone, managing money, etc.  
Self care ADL refer to bathing, dressing and undressing, feeding self, using the toilet, taking medications, and not bedridden.

#### 8.1.4 Attribution Assessment

The Principal Investigator will evaluate all AEs and assess their toxicity and attribution, if any, to study drug. The following criteria will define the attribution:

**Definite:** The AE is clearly related to the investigational agent.

**Probable:** The AE is likely related to the investigational agent.

**Possible:** The AE may be related to the investigational agent.

**Unlikely:** The AE is doubtfully related to the investigational agent.

**Unrelated:** The AE is NOT related to the investigational agent.

#### 8.1.5 Serious Adverse Event

A serious adverse event or experience (SAE) or serious adverse drug reaction (ADR) is any adverse event temporally associated with the subject's participation in research that meets any of the following criteria:

- Death;
- Is life-threatening (places the subject at immediate risk of death from the event as it occurred);

- Requires inpatient hospitalization or prolongation of existing hospitalization;\*
- Results in congenital anomaly/birth defect;
- Results in a persistent or significant disability/incapacity;
- Important medical events that may not result in death, be life-threatening, or require hospitalization may be considered a serious adverse drug experience when, based upon appropriate medical judgment, they may jeopardize the patient or subject and may require medical or surgical intervention to prevent one of the outcomes listed in the definition. For reporting purposes, also consider the occurrences of pregnancy as an event which must be reported as an important medical event.

\*Hospitalization for anticipated or protocol specified procedures such as administration of chemotherapy, central line insertion, metastasis interventional therapy, resection of primary tumor, or elective surgery, will not be considered serious adverse events.

